7.2 Assessing and Recording Adverse Events

An adverse event is defined as any untoward medical occurrence in a clinical investigation subject administered a medical device treatment and which does not necessarily have to have a causal relationship with this treatment. An adverse event can therefore be any unfavorable and unintended sign (including an abnormal laboratory finding, for example), symptom, or disease temporally associated with the use of a medicinal product or protocol specified procedure, whether considered related to the medicinal product or protocol specified procedure. Any worsening (i.e., any clinically significant adverse change in frequency and/or intensity) of a preexisting condition that is temporally associated with the use of the product, is also an adverse event.

Changes resulting from normal growth and development that do not vary significantly in frequency or severity from expected levels are not to be considered adverse events.

Examples of this may include, but are not limited to, teething, typical crying in infants and children and onset of menses or menopause occurring at a physiologically appropriate time.

Product includes any device, diagnostic agent, pharmaceutical product, biological product, or protocol-specified procedure, whether investigational (including sham or active comparator treatment) or marketed, manufactured by, licensed by, provided by, or distributed by the vendor for human use.

Adverse events may occur during clinical trials, or as prescribed in clinical practice, from inadequate therapeutic regimen (whether accidental or intentional), from abuse and from withdrawal.

Electronic reporting procedures can be found in the electronic data capture (EDC) entry guidelines. Paper reporting procedures can be found in the Investigator Trial File Binder (or equivalent).

7.2.1 Definition of an Over-treatment for this Protocol and Reporting of Over-treatment

In this trial, an over-treatment is any therapeutic regimen of higher intensity or of longer duration than the specified therapeutic regimen to be administered in a calendar day (accidental or intentional). If an adverse event(s) is associated with (“results from”) the over-treatment, the adverse event(s) is reported as a serious adverse event, even if no other seriousness criteria are met. If the therapeutic regimen meeting the protocol definition of over-treatment is taken without any associated clinical symptoms or abnormal laboratory results, the over-treatment is reported as a non-serious Event of Clinical Interest (ECI), using the terminology “accidental or intentional over-treatment without adverse effect.”

All reports of over-treatment with and without an adverse event must be reported by the investigator within 24 hours either by electronic media or paper. Electronic reporting procedures can be found in the electronic data capturing (EDC) entry guidelines. Paper reporting procedures can be found in the Investigator Trial File Binder (or equivalent).

7.2.2 Reporting of Pregnancy and Lactation

Female participants may screen for this study if:

- They are surgically sterile [have had a hysterectomy (uterus removed), bilateral oophorectomy (ovaries removed), or tubal ligation at least 6 months prior]
- They are of post-menopausal age and have not had a menstrual period for 12 months
- They have a vasectomized partner (performed at least 6 months prior) who has been documented to no longer produce sperm
- They are using a highly effective method of contraception to avoid pregnancy throughout the study and for 30 days after you complete this study.

Examples of acceptable forms of highly effective contraception include:

1. Established use of oral, injected or implanted hormonal methods of contraception plus use of a condom for your male partner.
2. Placement of an intrauterine device (IUD) or intrauterine system (IUS) plus use of a condom for your male partner.
3. True abstinence: When this is in line with your preferred and usual lifestyle

NOTE: Periodic abstinence (e.g., calendar, ovulation, symptothermal, post ovulation methods), condoms alone or double barrier are not acceptable methods of contraception.

Male participants must ensure a condom is used for all sexual intercourse as well as following the acceptable methods of contraception listed above for your female partner and ensuring that they are used for the entire duration of the study, and for at least 90 days after you complete this study.

Although pregnancy and lactation are not considered adverse events, it is the responsibility of investigators or their designees to report any pregnancy or lactation in a subject (spontaneously reported to them) that occurs during the trial.

7.2.3 **Immediate Reporting of Adverse Events**

7.2.3.1 **Serious Adverse Events**

A serious adverse event is any adverse event occurring at any therapeutic regimen or during any use of the product that:

- Results in death;
- Is life threatening;
- Results in persistent or significant disability/incapacity;
- Results in or prolongs an existing inpatient hospitalization;
- Is a congenital anomaly/birth defect;
- Is another important medical event.

Note: In addition to the above criteria, adverse events meeting either of the below criteria, although not serious per ICH definition, are reportable in the same timeframe as SAEs to meet certain local requirements. Therefore, these events are considered serious for collection purposes.

- Is a cancer;
- Is associated with an overdose.

Refer to [Table 6](#) for additional details regarding each of the above criteria.

For the time period beginning when the consent form is signed until treatment, any serious adverse event, or follow up to a serious adverse event, including death due to any cause, that occurs to any subject must be reported within 24 hours for weekly days or 72 days over the weekend if it causes the subject to be excluded from the trial, or is the result of a protocol-specified intervention, including but not limited to washout or discontinuation of usual therapy, diet, sham treatment or a procedure. The 24 hours for the site starts when the site becomes aware of the SAE. SAEs not reported will be considered a major protocol deviation.

For the time beginning at treatment allocation through 14 days following cessation of treatment, any serious adverse event, or follow up to a serious adverse event, including death due to any cause, whether or not related to the product, must be reported within 24 hours either by electronic media or paper. Electronic reporting procedures can be found in the EDC data entry guidelines. Paper reporting procedures can be found in the Investigator Trial File Binder (or equivalent).

Additionally, any serious adverse event, considered by an investigator who is a qualified physician to be related to the product that is brought to the attention of the investigator at any time outside of the time specified in the previous paragraph also must be reported immediately.

All subjects with serious adverse events must be followed up for outcome.

7.2.3.2. **Events of Clinical Interest (during the stimulation visit 2 (in the 1h after each stimulation))**

1. Agitation – daytime or nighttime
2. Confusion or cognitive impairment - daytime or nighttime

Regarding items #1 and 2 above, agitation, confusion or cognitive impairment should be considered an ECI if in the investigator's opinion an acute worsening from baseline has occurred, or there is an unusual or atypical presentation of symptoms for a given subject.

7.2.3.3 Protocol-Specific Exceptions to Serious Adverse Event Reporting

7.2.4 Evaluating Adverse Events

An investigator who is a qualified physician will evaluate all adverse events with respect to the elements outlined in [Table 4](#). The investigator's assessment of causality is required for each adverse event. Refer to [Table 4](#) for instructions in evaluating adverse events.

Table 4 Evaluating Adverse Events

Maximum Intensity	Mild	awareness of sign or symptom, but easily tolerated (for pediatric trials, awareness of symptom, but easily tolerated)
	Moderate	discomfort enough to cause interference with usual activity (for pediatric trials, definitely acting like something is wrong)
	Severe	incapacitating with inability to work or do usual activity (extremely distressed or unable to do usual activities)
Seriousness	A serious adverse event (SAE) is any adverse event occurring at any Therapeutic regimen or during any use of product that:	
	† Results in death ; or	
	† Is life threatening ; or places the subject, in the view of the investigator, at immediate risk of death from the event as it occurred [Note: This does not include an adverse event that, had it occurred in a more severe form, might have caused death.]; or	
	† Results in a persistent or significant disability/incapacity (substantial disruption of one's ability to conduct normal life functions); or	
	† Results in or prolongs an existing inpatient hospitalization (hospitalization is defined as an inpatient admission, regardless of length of stay, even if the hospitalization is a precautionary measure for continued observation. (Note: Hospitalization for an elective procedure to treat a pre-existing condition that has not worsened is not a serious adverse event. A pre-existing condition is a clinical condition that is diagnosed prior to the use of a Hospital del Mar neurosciences product and is documented in the patient's medical history.); or	
	† Is a congenital anomaly/birth defect (in offspring of subject taking the product regardless of time to diagnosis); or	
	Is a cancer (although not serious per ICH definition, is reportable within 24 hours to meet certain local requirements); or	
	Is associated with an over-treatment (whether accidental or intentional). Any adverse event associated with an over-treatment is considered a serious adverse event for collection purposes. An over-treatment that is not	

	associated with an adverse event is considered a non-serious event of clinical interest and must be reported within 24 hours.
	Other important medical events that may not result in death, not be life threatening, or not require hospitalization may be considered a serious adverse event when, based upon appropriate medical judgment, the event may jeopardize the subject and may require medical or surgical intervention to prevent one of the outcomes listed previously (designated above by a †).
Duration	Record the start and stop dates of the adverse event. If less than 1 day, indicate the appropriate length of time and units
Action Taken	Did the adverse event cause the product to be discontinued?
Relationship to Product	
Did the product cause the adverse event? The determination of the likelihood that the product caused the adverse event will be provided by an investigator who is a qualified physician. The investigator's signed/dated initials on the source document or worksheet that supports the causality noted on the AE form, ensures that a medically qualified assessment of causality was done. This initialed document must be retained for the required regulatory time frame. The criteria below are intended as reference guidelines to assist the investigator in assessing the likelihood of a relationship between the test drug and the adverse event based upon the available information
 
The following components are to be used to assess the relationship between the product and the AE; the greater the correlation with the components and their respective elements (in number and/or intensity), the more likely the product caused the adverse event:

Exposure	Is there evidence that the subject was actually exposed to the product such as: reliable history, acceptable compliance assessment (pill count, diary, etc.), expected pharmacological effect, or measurement of drug/metabolite in bodily specimen?
Time Course	Did the AE follow in a reasonable temporal sequence from administration of the product? Is the time of onset of the AE compatible with a drug-induced effect (applies to trials with investigational medicinal products)?
Likely Cause	Is the AE not reasonably explained by another etiology such as underlying disease, other drug(s)/vaccine(s), or other host or environmental factors

Relationship to the Product (continued)	The following components are to be used to assess the relationship between the product and the AE (continued)	
	Dechallenge	
Was the product discontinued or dose/exposure/frequency reduced?
 
If yes, did the AE resolve or improve?
 
If yes, this is a positive dechallenge. If not, this is a negative dechallenge.
 
(Note: This criterion is not applicable if: (1) the AE resulted in death or permanent disability; (2) the AE resolved/improved despite continuation of the product; (3) the trial is a single-Therapeutic regimen drug trial); or (4) product(s) is/are only used one time.)

	Rechallenge	
Was the subject re-exposed to the product in this trial?
 
If yes, did the AE recur or worsen?
 
If yes, this is a positive rechallenge. If not, this is a negative rechallenge.
 
(Note: This criterion is not applicable if: (1) the initial AE resulted in death or permanent disability, or (2) the trial is a single-Therapeutic regimen drug trial); or (3) product(s) is/are used only one time.)
 
NOTE: IF A RECHALLENGE IS PLANNED FOR AN ADVERSE EVENT WHICH WAS SERIOUS AND WHICH MAY HAVE BEEN CAUSED BY THE PRODUCT, OR IF RE-EXPOSURE TO THE PRODUCT POSES ADDITIONAL POTENTIAL SIGNIFICANT RISK TO THE SUBJECT THEN THE RECHALLENGE MUST BE APPROVED IN ADVANCE BY THE CLINICAL DIRECTOR AND THE INSTITUTIONAL REVIEW BOARD/INDEPENDENT ETHICS COMMITTEE.

	Consistency with Trial Treatment Profile	Is the clinical/pathological presentation of the AE consistent with previous knowledge regarding the product or drug class pharmacology or toxicology?
The assessment of the relationship will be reported on the case report forms /worksheets by an investigator who is a qualified physician according to his/her best clinical judgment, including consideration of the above elements.		
Record one of the following:		Use the following scale of criteria as guidance (not all criteria must be present to be indicative of a

	product relationship).
Yes, there is a reasonable possibility of product relationship.	There is evidence of exposure to the product. The temporal sequence of the AE onset relative to the administration of the product is reasonable. The AE is more likely explained by the product than by another cause.
No, there is not a reasonable possibility of product relationship	Subject did not receive the product OR temporal sequence of the AE onset relative to administration of the product is not reasonable OR the AE is more likely explained by another cause than the product. (Also entered for a subject with over-treatment without an associated AE.)

7.2.5 Investigator Responsibility for Reporting Adverse Events

All Adverse Events will be reported to the Ethical Committee of Hospital del Mar and investigators in accordance with all applicable global laws and regulations, i.e., per ICH Topic E6 (R1) Guidelines for Good Clinical Practice.

8.0 STATISTICAL ANALYSIS PLAN

8.1 Statistical Analysis Plan Summary

Considering this is the first study in a very small population for assessing the safety and tolerability and getting insights on the efficacy, results will be provided only as a descriptive statistical analysis

Table 5 Statistical analysis plan

Study Design Overview	Modulation of the motor pathway by Transcranial Pulse Stimulation in people with ALS: a pilot randomized trial
Treatment Assignment	Active stimulation: 36,000 pulses in 2 weeks distributed in 6 sessions Sham: stimulations using a sound blocker (membrane filled with air)
Analysis Populations	Intention to treat Per Protocol
Primary Endpoint(s)	Stage 1. Change in the motor cortex excitability threshold from baseline to week 8. Stage 2. Change from baseline to month 6 in the ALS functional rating scale-revised (ALSFRS-R) total score.
Key Secondary Endpoints	Secondary stage 1: 1. Change in the motor cortex excitability (paired-pulse transcranial magnetic stimulation (ppTMS): motor evoked potential (MEP) amplitudes, resting motor threshold, intra-cortical facilitation (ICF) and short intracortical inhibition (SICI)), from baseline to week 4 2. Change plasma NfL levels from baseline to week 4 and 8 3. Changes in muscle strength, assessed by MRC sum score from baseline to week 4 and 8 4. Changes in hand-held dynamometry from baseline to week 4 and 8 Secondary stage 2: 1. Differences (treated vs sham) and change (from baseline to end of the study (month 6)) in the slow vital capacity (SVC) 2. Differences (treated vs sham) and change (from baseline to end of the study (month 6)) in plasma NfL levels or other biomarkers from exploratory stage 1 if found significant

	
3. Differences (treated vs sham) and change (from baseline to end of the study (month 6)) in cortical hyperexcitability (MEP amplitudes, resting motor threshold, ICF and SICI)
 
4. Changes in muscle strength, assessed by MRC sum score from baseline to end of the study (month 6)
 
5. Changes in hand-held dynamometry, from baseline to end of the study (month 6)

Exploratory endpoints	
Exploratory stage 1
 
1. Changes in SOD1, Ataxin 2, C9orf72, UNC13A, TDP43, NfL and NfH levels in extracellular vesicles of neuronal origin (nEVs) collected from plasma from baseline to week 4 and 8
 
Exploratory stage 2
 
1. Differences (treated vs sham) and change (from baseline to end of the study (month 6)) in biomarker levels in nEVs collected from plasma that were informative in stage 1 from baseline to week 4 and 8

Statistical Methods for Key Efficacy Analyses	Changes on ALSFRS-R, motor threshold, biomarker levels before and after stimulation will be assessed with ANCOVA test.
Statistical Methods for Key Safety Analyses	Descriptive statistics
Interim Analyses	No interim analysis for efficacy or safety is planned for this study.
Multiplicity	Not planned
Sample Size and Power	Considering that this is a pilot study, and no previous data is available for this intervention, a convenience sample size of 10 subjects for stage 1 and 40 subjects for stage 2 has been defined. Using the results from the CENTAUR trial ¹ in patients with ALS, a sample size of 6 patients per arm provided a 90% to detect differences by week 24 with alpha 0.05.

8.2 Responsibility for Analyses

The statistical analysis of the data obtained from this study will be the responsibility of the Principal Investigator.

8.3 Hypotheses

Objectives and hypotheses of the study are stated in Section 3.

8.4 Analysis Endpoints

Key efficacy and safety endpoints that will be evaluated for within- and/or between-TPS protocols are listed below, followed by the descriptions of the derivations of selected endpoints.

8.4.1. Efficacy Endpoints

Rationale for the key efficacy endpoints is given in Section 4.2.3.1 and an initial description of the efficacy measures is included in Section 7.1.2.2. In general, if a baseline value exists for a particular efficacy measure, then the change from baseline in that value will be evaluated.

Primary Endpoint

- Stage 1. Change in the motor cortex excitability threshold from baseline to week 8.
- Stage 2. Change from baseline to month 6 in the ALS functional rating scale-revised (ALSFRS-R) total score.

Secondary Endpoint

Secondary stage 1:

1. Change in the motor cortex excitability (paired-pulse transcranial magnetic stimulation (ppTMS): motor evoked potential (MEP) amplitudes, resting motor threshold, intra-cortical facilitation (ICF) and short intracortical inhibition (SICI)), from baseline to week 4
2. Change plasma NfL levels from baseline to week 4 and 8

3. Changes in muscle strength, assessed by MRC sum score from baseline to week 4 and 8
4. Changes in hand-held dynamometry from baseline to week 4 and 8

Secondary stage 2:

1. Differences (treated vs sham) and change (from baseline to end of the study (month 6)) in the slow vital capacity (SVC)
2. Differences (treated vs sham) and change (from baseline to end of the study (month 6)) in plasma NfL levels or other biomarkers from exploratory stage 1 if found significant
3. Differences (treated vs sham) and change (from baseline to end of the study (month 6)) in cortical hyperexcitability (MEP amplitudes, resting motor threshold, ICF and SICI)
4. Changes in muscle strength, assessed by MRC sum score from baseline to end of the study (month 6)
5. Changes in hand-held dynamometry, from baseline to end of the study (month 6)

8.4.2 Safety Endpoints

Presence of serious adverse events (together with items of special attention)

An initial description of the safety measures is included in Sections 7.1.2.1, 7.1.2.2.10 and 7.1.3. Safety and tolerability will be assessed by statistical and clinical review of the following data collected throughout the study: adverse experiences (AEs), and treatment-emergent suicidality. The Columbia-Suicide Severity Rating Scale (C-SSRS) will be used to ascertain and document the occurrence of suicidal events (i.e., ideation and behavior) systematically and prospectively. Responses on the C-SSRS are classified according to 11 pre-specified categories as described in Appendix 12.14.

The primary time for safety analyses is Visit 2; Safety endpoints are classified into 2 tiers (see Statistical Methods for Key Safety Analyses in Section 8.1 for Tier definitions).

Tier 1 Safety Endpoints include (the proportion of subjects with):

1. Any AE
2. Any Serious AE
3. Any treatment-Related AE

4. Any Serious and treatment-Related AE

5. Discontinuation due to AE

Tier 2 Safety Endpoints include:

1. Specific AEs, SOC AEs or PDLCs which have incidence in all 3 subjects.

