Measurements & Procedures	
 1. ALSFRS-R 2. SVC 3. MRC sum score 4. Hand-held Dynamometry 5. Motor cortex excitability by TMS 6. Plasma NfL levels 7. Blood: isolation nEVs and biomarker quantification (SOD1, Ataxin 2, C90rf72, UNC13A, TDP43, stathmin 2, NfL and NfH) 8. Brain MRI for neuronavigation 9. TPS stimulations (6 sessions of 20 min each in 2 weeks)
Study Product / Intervention	Neurolith is a medical device delivering transcranial pulse stimulations under neuronavigation guidance.
Controls	ALS patients allocated to sham stimulations. Sham treated patients will be offered to receive TPS therapy in the Open Label Extension phase (OLE) of the trial for ethical purposes.
Number of Participants & Rationale	
Stage 1: n=10
 
Stage 2: n=40 (randomization 2:1 active vs sham stimulation)
 
Rationale for sample size: this is an exploratory sample likely to be informative for experience in planning for future trials.

Study Duration:	
24 months
 
Stage 1: 6 months
 
Stage 2: 3 months recruitment, 6 months randomized phase, 6 months OLE, 3-month analysis and clinical scientific report

Timelines:	
Stage 1:
 
 ● First Patient First Visit (FPFV): September 1st, 2024 ● Last Patient Last Visit (LPLV): February 1st, 2025 
Stage 2:
 
 ● First Patient First Visit (FPFV): March 1st, 2025 ● Last Patient Last Visit (LPLV): October 1st, 2026
Study Schedule:	
Patients are recruited from the ALS center at Hospital del Mar from patients diagnosed with ALS and referrals provided by the local ALS foundation (Miquel Valls Foundation)
 
Stage 1: V1: informed consent, inclusion/exclusion criteria, TMS cortex excitability, brain MRI (for neuronavigation) can be conducted at any time between Visit 1 and 2; V2: stim; V3: TMS and biomarkers assessment week 4; V4: TMS and biomarkers assessment week 8.

	Stage 2: V1: informed consent, inclusion/exclusion criteria, TMS cortex excitability, brain MRI (for neuronavigation) can be conducted at any time between Visit 1 and 2; V2: randomization and baseline; V3-5: stim, biomarkers and scales; V6-V7: open label extension
Study Center:	ALS center and Neuromodulation center. Hospital del Mar – Pompeu Fabra University, Barcelona, Spain

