4.2.3.2 Safety Endpoints

The safety and tolerability of TPS will be continuously assessed throughout the study via Adverse Event reporting, and vital signs will be assessed at every trial visit. The Columbia-

Suicide Severity Rating Scale (C-SSRS) will be conducted at the baseline and end of the treatment to prospectively assess for the emergence of suicidal ideation and behavior.

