5.2.1 Therapeutic regimen Selection: TPS stimulation protocols

20 min stimulation with a maximum of 6,000 pulses and maximum of 0.25 mJ/mm² per session. 6 Sessions in 2 weeks per treatment period followed with a single stimulation session every 2 months (2 additional sessions by month 2 and 4).

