7.1.5.1.2 Visit 2: baseline

Patients will be randomized to either treatment or sham stimulation and assigned a code (except for patient sin stage 1, which are not randomized, and all receive active stimulation). Before starting stimulation, the researcher will conduct a vital signs, physical exam and neurological examination. Urine (50 ml) and blood (20 ml) will be collected and stored. Then, the patient will be subjected to the first TPS stimulations (a 20 min stimulations).

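### Section 8.4.2 sets the primary time for safety analyses at Visit 2, which contradicts the promised review of safety data from the whole study and leaves out most exposure and follow-up

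*Protocol*

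**What the plan says.** Section 8.4.2 of the protocol fixes one time point: "The primary time for safety analyses is Visit 2". No other section changes or explains it.

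Other statements point to the whole study. Section 4.2.3.2 says: "The safety and tolerability of TPS will be continuously assessed throughout the study via Adverse Event reporting". Sections 8.4.2 and 8.6 both describe statistical and clinical review of adverse events and suicidality data gathered over the full study, with no limit by visit. Section 7.2.3.1 has serious adverse events reported from treatment allocation to 14 days after treatment stops. Section 4.2.2.1 gives the collection of more safety data as one purpose of the open-label extension.

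The protocol describes Visit 2 in several ways:

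- Section 7.1.5.1.2 makes it the baseline visit, with randomization in Stage 2. After the examinations, "Then, the patient will be subjected to the first TPS stimulations".
- The Stage 2 synopsis in section 1.0 reads: "V2: randomization and baseline; V3-5: stim, biomarkers and scales; V6-V7: open label extension". No stimulation is shown at V2.
- The Stage 1 synopsis reads: "V2: stim; V3: TMS and biomarkers assessment week 4; V4: TMS and biomarkers assessment week 8". V2 is the only stimulation visit listed.
- Section 7.1.4.1 speaks of three planned stimulations within visit 2. Section 7.2.3.2 speaks of the hour after each stimulation at visit 2, and section 7.1.2.2 of an examination by the end of visit 2.
- The flow chart in section 6.0 marks stimulation at screening, at Visit 2 and at Visits 3-5.

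**The concern.** Section 3.4 states a safety hypothesis: TPS is safe and well tolerated. The analysis labelled primary should be able to test that against the treatment as given. A time point at the start of treatment cannot, because it comes before most sessions and before nearly all follow-up.

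The planned measures also fit Visit 2 poorly:

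- Section 8.5.1 requires a vital-sign measurement after at least one stimulation, but section 7.1.5.1.2 describes vital signs at Visit 2 only before stimulation.
- Section 7.1.5.1.3 places the C-SSRS after each six-session period, so a Visit 2 reading is in effect a baseline.
- Discontinuation due to an adverse event, a Tier 1 endpoint, accrues over a course of treatment and not over one visit.

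At stake is which result is reported as the primary safety result. Two analysts following the protocol could produce very different primary tables, one limited to Visit 2 and one covering the study.

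**Working it through.** **Planned exposure.** The inputs are "Active stimulation: 36,000 pulses in 2 weeks distributed in 6 sessions" (section 8.1) and "20 min stimulation with a maximum of 6,000 pulses and maximum of 0.25 mJ/mm² per session" (section 5.2.1). Check: 6 sessions × 6,000 pulses = 36,000, which reproduces the plan's figure. Sections 5.2.1 and 5.2.2 add single sessions at months 2 and 4, so the blinded period has 6 + 2 = 8 sessions.

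**Share of sessions at Visit 2** (sessions at Visit 2 ÷ planned sessions), by reading:

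| Reading of Visit 2 | Initial course of 6 | Blinded period of 8 |
|---|---|---|
| First session only (7.1.5.1.2) | 1/6 = 16.7% | 1/8 = 12.5% |
| No stimulation (Stage 2 synopsis) | 0% | 0% |
| Three stimulations (7.1.4.1) | 3/6 = 50% | 3/8 = 37.5% |

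For Stage 1 alone, the synopsis could mean that V2 holds the whole course. The loss of exposure would then not apply to Stage 1, but the follow-up to week 8 would still fall outside.

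**Share of follow-up at Visit 2**, taken as one day ÷ (days from Visit 2 to the end of the period + 1):

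- Stage 2, about 26 weeks: 1/(182 + 1) = 0.5%.
- Stage 2, if the flow chart's week 16 ends the blinded period (week 1 to week 16): 1/(105 + 1) = 0.9%.
- Stage 1, to week 8: 1/(56 + 1) = 1.8%.

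**Illustration in patients (assumed rates).** The protocol gives no adverse event rate. Assume that a fraction p of active patients has an event over the blinded period, with equal risk at each of 8 sessions and one session at Visit 2. The risk per session is 1 − (1 − p)^(1/8). The number of active patients is itself in conflict: section 5.3 gives 1:1 (40/2 = 20), and section 1.0 gives 2:1 (40 × 2/3, about 27).

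| Assumed p | Risk per session | 1:1, 20 active: Visit 2 vs whole period | 2:1, 27 active: Visit 2 vs whole period |
|---|---|---|---|
| 10% | 1.3% | 0.3 vs 2 | 0.4 vs 2.7 |
| 30% | 4.4% | 0.9 vs 6 | 1.2 vs 8.1 |
| 50% | 8.3% | 1.7 vs 10 | 2.2 vs 13.5 |

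Under these assumptions, the Visit 2 analysis expects between about one eighth and one sixth of the affected patients, whichever ratio applies. Equal risk per session builds in no delayed or cumulative effect; with such effects the share at Visit 2 would be smaller.

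**The case against.** The strongest reply is that safety is not analysed at Visit 2 alone. Sections 8.4.2 and 8.6 promise statistical review, not just collection, of data from the whole study. The safety table in section 8.6 has no visit restriction, and serious adverse events are reported well beyond Visit 2. This stands. A reader might infer that later events would go unanalysed, or that the safety results as a whole rest on one session. The documents do not support that: only the label of primary attaches to Visit 2, in conflict with the surrounding text.

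A second reply is that the sentence is probably carried over from another design. The several-stimulation visit 2 in sections 7.1.4.1 and 7.2.3.2 points that way. So does the Tier 2 wording in section 8.4.2, which refers to all 3 subjects in a trial of 10 + 40. This is plausible and tells against reading the sentence as a deliberate choice of a favourable time point. It explains the error without removing it.

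A third reply is that little depends on the time point. The primary endpoints are efficacy measures, section 8.1 calls the results descriptive, section 8.7 plans no interim analysis, and section 5.11 sets no criterion for early termination. Stage 1 has no comparison group. This limits the consequence to reporting and interpretation.

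**Conclusion.** The point holds as an internal contradiction with a poorly chosen primary time. Section 8.4.2 names Visit 2, while sections 4.2.3.2, 8.4.2 and 8.6 speak of the whole study. The excluded share depends on the reading: Visit 2 holds 0, 1 or 3 of the 8 blinded-period sessions (0%, 12.5% or 37.5%) and about 0.5% to 0.9% of the Stage 2 follow-up if it is one day. No reading makes it cover the Stage 2 blinded period or the time after stimulation, and that conclusion needs no assumed event rate.

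Two figures should not be taken as firm. The 12.5% follows from the procedures text and is not agreed across the protocol. The patient counts rest on assumed risks, equal risk per session and an allocation ratio that the protocol states in two ways; they show direction and rough size only.

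**What to change.** Replace the sentence in section 8.4.2 with wording such as: The primary safety analysis covers all events from the first stimulation to the end-of-stage visit in Stage 1, and to the end of the blinded period in Stage 2; events in the open-label extension are summarised separately. Visit 2 can remain at most as a summary of acute tolerability.

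Two reconciliations must come with it:

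- **End dates.** The flow chart ends Stage 1 at week 4 and the blinded period at week 16, while the endpoints and synopsis use week 8 and month 6. The sponsor must settle these and then state the dates in the new sentence.
- **Meaning of Visit 2.** The uses in sections 1.0, 6.0, 7.1.2.2, 7.1.4.1, 7.1.5.1.2 and 7.2.3.2 must be brought into line with one another.

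The cost is a few linked text edits. Adverse events are already collected over the wider window. One limit remains: the flow chart schedules no C-SSRS at the Stage 1 end visit or at the end of the blinded period, so the suicidality part of the window stops at its last scheduled assessment, and the text should say so.
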